Observational Study Information

Title	Pattern of use of Direct Oral Anticoagulants in Non-valvular Atrial Fibrillation patients in UK general practices
Protocol version identifier	1.0
Date of last version of protocol	24.02.2017
IMPACT study number	19330
Study type/Study phase	 non-PASS  PASS Joint PASS:  YES  NO
Active substance	B01A F DIRECT FACTOR Xa INHIBITORS (B01A F01 RIVAROXABAN, B01A F02 APIXABAN) and B01A E07 DABIGATRAN
Medicinal product	Xarelto, Pradaxa, and Eliquis
Marketing authorization holder(s)	Bayer AG, 51368 Leverkusen
Research question and objectives	
Primary Objective
 
• To provide baseline characteristics of NVAf patients who are prescribed with any of the three DOACs (rivaroxaban, dabigatran and apixaban) for the first time for stroke prevention, and contrast with the corresponding characteristics of patients in clinical trials.• To assess the pattern of use (daily dose, dose posology, treatment duration, naïve status) of rivaroxaban, dabigatran and apixaban in UK for stroke prevention in NVAf patients• To assess the proportion of NVAf patients with renal impairment who are prescribed with rivaroxaban, dabigatran, and apixaban at index date including their treatment characteristics (daily dose, dose posology, duration). 
Secondary Objective

	
To determine time-trends in the characteristics of first-time use of rivaroxaban, dabigatran and apixaban in NVAf patients.
Country(-ies) of study	United Kingdom
Author	[name] [name] Spanish Centre for Pharmacoepidemiologic Research (CEIFE) [name] [contact] Email: [contact]

Marketing authorization holder

Marketing authorization holder(s)	Bayer AG, 51368 Leverkusen
MAH contact person	[name] Epidemiology Bayer AG 13353 Berlin [contact] Email: [contact]

The study will be conducted in compliance with the protocol and any applicable regulatory requirements.

Throughout this document, symbols indicating proprietary names (®, TM) may not be displayed. Hence, the appearance of product names without these symbols does not imply that these names are not protected.

1. Table of Contents

Observational Study Information.....	1
1. Table of Contents	3
2. List of abbreviations	5
3. Responsible parties	6
Study initiator and funder / MAH	6
Collaborators / Committees	6
4. Abstract.....	7

SRC Scientific Research Committee
STROBE Strengthening the Reporting of Observational Studies in Epidemiology
THIN The Health Improvement Network
UK United Kingdom
VKAs Vitamin K antagonists

3. Responsible parties

Study initiator and funder / MAH

Function: Study conduct responsible and Study Epidemiologist

Name: [name]

Email: [contact]

Function: Study Medical Expert

Name: [name]

Function: Study Safety Lead

Name: [name]

Function: Study Statistician

Name: [name]

Function: Real Life Evidence Strategy and Outcomes Data Generation

Name: [name]

Function: Bayer UK – Local Study Unit, Medical Affairs

Name: [name]

Function: Bayer UK – Medical Advisor

Name: [name]

Collaborators / Committees

Principal Investigator: [name] [name]

Co-investigator: [name]

Spanish Centre for Pharmacoepidemiologic Research (CEIFE)

[name]

[contact]

Email: [contact]

4. Abstract

Title

Pattern of use of Direct Oral Anticoagulants in Non-valvular Atrial Fibrillation patients in UK general practices

v 1.0, 24 February 2017

[name] [name]

Spanish Centre for Pharmacoepidemiologic Research (CEIFE), Madrid, Spain

Rationale and background

Individualized anticoagulant treatment should be based on patients' age, renal function, comorbidities, and concomitant treatments. The DOACs are new agents with several advantages including use of fixed-dosing with no need for INR monitoring, few interactions etc. The lack of effective antidote for some of them, their cost, or uncertainties in patients with kidney disease, and associated risk of bleeding may explain reservations in their widespread use (Hinojar et al. 2015).

There is a limited data on prescription and usage patterns of DOACs in routine care for stroke prevention in non-valvular atrial fibrillation (NVAF). Monitoring the usage patterns of DOACs is essential to study compliance with labelling information.

Research question and objectives

This population-based descriptive study will characterize first-time users of three DOACs in NVAF patients for stroke prevention including those renal impaired. Additionally, it will assess patterns of drug utilization in routine general practice in the UK, using the Clinical Practice Research Datalink (CPRD) and The Health Improvement Network (THIN).

Primary Objective

- To provide baseline characteristics of NVAF patients who are prescribed with any of the three DOACs (rivaroxaban, dabigatran and apixaban) for the first time for stroke prevention, and contrast with the corresponding characteristics of patients in clinical trials.
- To assess the pattern of use (daily dose, dose posology, treatment duration, naïve status) of rivaroxaban, dabigatran and apixaban in UK for stroke prevention in NVAF patients
- To assess the proportion of NVAF patients with renal impairment who are prescribed with rivaroxaban, dabigatran, and apixaban at index date including their treatment characteristics (daily dose, dose posology, duration).

Secondary Objective

- To determine time-trends in the characteristics of first-time use of rivaroxaban, dabigatran and apixaban in NVAF patients.

Study design

This is a population-based retrospective cohort study designed to assess the characteristics of patients and patterns of drug utilization in new users of DOACs in the UK by merging the CPRD and THIN databases.

The study enrollment period extends from 1st January 2011 up to last available database extraction (at time of writing, May 2016 in THIN and in CPRD).

Among the source population resulting from the combination of THIN and CPRD databases, we will ascertain three separate cohorts of first-time users of rivaroxaban, apixaban and dabigatran using the date of first prescription (index date) of the respective drug (index drug).

This study will apply a new-users (initiators) design (Ray, 2003). New users are individuals starting a study medication for the first time ever recorded in the database. Yet, they may have used the other study medications before index date and therefore classified as non-naïve. New-users without any history of any oral anticoagulant would be classified as naïve.

Population

All patients aged 18 and above and who have been enrolled in the databases for at least 1 year and had their first prescription recorded in the databases at least 1 year ago will be included in source population. A patient will be considered eligible to enter a study cohort as a first-time user of one of the study drugs when he or she has a first prescription of the drug recorded during the enrolment period. Among the three study cohorts, we will further identify patients with Non-valvular Atrial Fibrillation (NVAF).

Variables

Detailed descriptive variables including baseline characteristics will be captured for the population, including co-medications and comorbidities. Dose, posology, duration of study drug and other anticoagulant before index date including naïve/non-naïve status. Renal disease using estimated glomerular filtration rate (eGFR) as well as ACR (Albumin/Creatinine Ratio) where available. Also, risk scores, lifestyle factors and healthcare utilization.

Data sources

THIN - The population included in THIN is representative of the UK as a whole in terms of age, sex and geographic distribution. THIN now collects data from 570 practices, covering 6% of the general population of the UK population.

CPRD – It contains diagnostic and prescribing information recorded by GPs as part of their routine clinical practice in the UK. The CPRD has information on 5.4 million individuals (active contributors), which represents approximately 9% of the UK population.

Study size

THIN version1605: The prevalence of NVAF among patients 18+ and register with GP for at least a year is 1.89% (N= 74319).

CPRD GOLD 2014: The prevalence of AF in all ages was 2.47% in men and 1.56 % in women.

Data analysis

Describe the three study cohorts i.e. patients prescribed with rivaroxaban, dabigatran, apixaban by baseline characteristics, use of medications, comorbidities and healthcare utilization services among the three study cohorts and contrast them with the baseline characteristics of patients in clinical trials.

Use of study medications: Dose at first Rx, dose posology, duration of treatment (time on index medication), discontinuation, switch to another study drug.

To assess the proportion of patients that are dosed in accordance and non-accordance to label, in study population and in subset of patients with renal impairment

Milestones

The project is planned to begin in February 2017 and will end in April 2017

5. Amendments and updates

None

6. Milestones

This study will be conducted between January 2017 and April 2017

Milestone	Project timeline
Protocol development and submission for review and comment	By end December 2016
Ethics Submission & Approval	By end January 2017
Data Extraction	March 2017
Data Analysis and reporting	April-May 2017

7. Rationale and Background

Vitamin K antagonists (VKAs) have been the standard treatment for antithrombotic prevention in atrial fibrillation (AF) in the last 60 years (NICE, 2016). Direct oral anticoagulants (DOACs) have shown to have a favourable balance between efficacy and safety compared with VKAs, and three (rivaroxaban, dabigatran, and apixaban) are now available and approved in the United Kingdom (UK) for the prevention of stroke in non-valvular AF (NVAF) patients.

Two classes of DOACs are currently available, the oral direct thrombin inhibitors (DTIs; e.g. dabigatran) and oral direct factor Xa inhibitors (e.g. rivaroxaban, apixaban, and edoxaban). Unlike VKAs, which block the formation of multiple active vitamin K-dependent coagulation factors (factors II, VII, IX, and X), these drugs block the activity of one single step in the coagulation cascade.

Individualized anticoagulant treatment should be based on patients' age, renal function, comorbidities, and concomitant treatments. The DOACs are new agents with several advantages including use of fixed-dosing with no need for INR monitoring, few interactions etc. The lack of effective antidote for some of them, their cost, or uncertainties in patients with kidney disease, and associated risk of bleeding may explain reservations in their widespread use (Hinojar et al. 2015).

There is a limited data on prescription and usage patterns of DOACs in routine care for stroke prevention in non-valvular atrial fibrillation (NVAF). Monitoring the usage patterns of DOACs is essential to study compliance with labelling information.

8. Research question and objectives

This population-based descriptive study will characterize first-time users of three DOACs in NVAF patients for stroke prevention including those renal impaired. Additionally, it will assess patterns of drug utilization in routine general practice in the UK, using the Clinical Practice Research Datalink (CPRD) and The Health Improvement Network (THIN).

8.1 Primary Objective

- To provide baseline characteristics of NVAF patients who are prescribed with any of the three DOACs (rivaroxaban, dabigatran and apixaban) for the first time for stroke prevention, and contrast with the corresponding characteristics of patients in clinical trials.
- To assess the pattern of use (daily dose, dose posology, treatment duration, naïve status) of rivaroxaban, dabigatran and apixaban in UK for stroke prevention in NVAF patients
- To assess the proportion of NVAF patients with renal impairment who are prescribed with rivaroxaban, dabigatran, and apixaban at index date including their treatment characteristics (daily dose, dose posology, duration).

8.2 Secondary Objective

To determine time-trends in the characteristics of first-time use of rivaroxaban, dabigatran and apixaban in NVAF patients.

9. Research methods

9.1 Study design

This is a population-based retrospective cohort study designed to assess the characteristics of patients and patterns of drug utilization in new users of DOACs in the UK.

The study enrollement period extends from 1st January 2011 up to last available database extraction (at time of writing, May 2016 in THIN and in CPRD).

Among the source population resulting from the combination of THIN and CPRD databases, we will ascertain three separate cohorts of first-time users of rivaroxaban, apixaban and dabigatran using the date of first prescription (index date) of the respective drug (index drug).

This study will apply a new-users (initiators) design (Ray et al, 2003). New users are individuals starting a study medication for the first time ever recorded in the database. Yet, they may have used the other study medications before index date and therefore classified as non-naïve. New-users without any history of any oral anticoagulant would be classified as naïve.

All patients aged 18 and above and who have been enrolled in the databases for at least 1 year and had their first prescription recorded in the databases at least 1 year ago will be included in source population. A patient will be considered eligible to enter a study cohort as a first-time user of one the study drugs when he or she has a first prescription of the drug recorded during the enrolment period.

Patients who have any record of being prescribed their index drug prior to the enrolment period or who qualify as members of more than one cohort on the same day, will be excluded. If a patient qualifies as first-time user of more than one study drug during the enrolment period, with different index dates, she/he will be assigned to the cohort of study drug first prescribed during the enrolment period, with the date of this prescription being the index date. (eg mutually exclusive cohorts)

Among the three study cohorts, we will further identify patients with NVAF defined as:-

Patients with a record of Atrial fibrillation (AF) any time prior index date or within the 2 weeks after the index date, and free of valvular replacement or mitral stenosis prior to index date or 2 weeks after index-date

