9.1.1 Primary end-points

1. Baseline characteristics of NVAF patients in the UK prescribed any of the three direct oral anticoagulants (DOACs) (rivaroxaban, dabigatran and apixaban) for the first time for stroke prevention
2. Daily dose, dose posology, naïve status, treatment duration of DOACs for stroke prevention in NVAF patients including those with renal impairment

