Annex 3. Additional information

List of Read Codes

Table S1.

Multilex code	BNF-code	Generic Name	ATC	ATC name	BCD	BCD name
53246979	02.08.02.00	Apixaban 5mg tablets	B01A	ANTITHROMBOTIC AGENTS	60396	APIXABAN
53247979	02.08.02.00	Apixaban 5mg tablets	B01A	ANTITHROMBOTIC AGENTS	60396	APIXABAN
81167998	02.08.02.00	Apixaban 2.5mg tablets	B01A F02	APIXABAN	60396	APIXABAN
81168998	02.08.02.00	Apixaban 2.5mg tablets	B01A F02	APIXABAN	60396	APIXABAN
81214998	02.08.02.00	Dabigatran etex150mg cap	B01A E07	DABIGATRAN ETEXILATE	60278	DABIGATRAN
81215998	02.08.02.00	Dabigatran etexilate 150mg caps	B01A E07	DABIGATRAN ETEXILATE	60278	DABIGATRAN
83971998	02.08.02.00	Dabigatran etexilate 110mg caps	B01A E07	DABIGATRAN ETEXILATE	60278	DABIGATRAN
83972998	02.08.02.00	Dabigatran etexilate 75mg caps	B01A E07	DABIGATRAN ETEXILATE	60278	DABIGATRAN
83973998	02.08.02.00	Dabigatran etexilate 75mg caps	B01A E07	DABIGATRAN ETEXILATE	60278	DABIGATRAN
83974998	02.08.02.00	Dabigatran etexilate 110mg caps	B01A E07	DABIGATRAN ETEXILATE	60278	DABIGATRAN
59454978	02.08.02.00	Rivaroxaban 2.5mg tablets	B01A F01	RIVAROXABAN	60320	RIVAROXABAN
60767979	02.08.02.00	Rivaroxaban 20mg tablets	B01A F01	RIVAROXABAN	60320	RIVAROXABAN
60768979	02.08.02.00	Rivaroxaban 20mg tablets	B01A F01	RIVAROXABAN	60320	RIVAROXABAN
60769979	02.08.02.00	Rivaroxaban 15mg tablets	B01A F01	RIVAROXABAN	60320	RIVAROXABAN
60770979	02.08.02.00	Rivaroxaban 15mg tablets	B01A F01	RIVAROXABAN	60320	RIVAROXABAN
80953998	02.08.02.00	Rivaroxaban 20mg tablets	B01A F01	RIVAROXABAN	60320	RIVAROXABAN
80954998	02.08.02.00	Rivaroxaban 20mg tablets	B01A F01	RIVAROXABAN	60320	RIVAROXABAN
80955998	02.08.02.00	Rivaroxaban 15mg tablets	B01A F01	RIVAROXABAN	60320	RIVAROXABAN
80956998	02.08.02.00	Rivaroxaban 15mg tablets	B01A F01	RIVAROXABAN	60320	RIVAROXABAN
83418998	02.08.02.00	Rivaroxaban 10mg tablets	B01A F01	RIVAROXABAN	60320	RIVAROXABAN
83425998	02.08.02.00	Rivaroxaban 10mg tablets	B01A F01	RIVAROXABAN	60320	RIVAROXABAN

Table S2:

Operational definitions for subpopulations:

Non-valvular Atrial Fibrillation (NVAf)	Patients with a record of Atrial fibrillation (AF) any time prior index date or within the 2 weeks after the index date, and free of valvular replacement or mitral stenosis (see table codes below) prior to index date or 2 weeks after index-date

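### The NVAF definition does not check why the DOAC was started, so courses given for another indication can enter results described as stroke prevention

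*Protocol*

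**What the plan says.** Section 8.1 sets the target. The first primary objective describes NVAF patients prescribed a DOAC "for the first time for stroke prevention". The second covers the pattern of use "in UK for stroke prevention in NVAF patients". Section 9.1.1 carries this into both end-points, the second being "Daily dose, dose posology, naïve status, treatment duration of DOACs for stroke prevention in NVAF patients including those with renal impairment".

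Section 9.1 sets the cohort. A patient enters when "he or she has a first prescription of the drug recorded during the enrolment period". There is no condition on indication, strength or intended length. The cohort-level exclusions are prior use of the index drug and same-day entry to two cohorts. NVAF is then applied as a filter: "Among the three study cohorts, we will further identify patients with NVAF defined as", followed by "Patients with a record of Atrial fibrillation (AF) any time prior index date or within the 2 weeks after the index date" and freedom from valve replacement or mitral stenosis up to 2 weeks after index. Table S2 in Annex 3 repeats the rule unchanged.

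Section 9.7 plans tables of dose at first prescription, posology, duration, discontinuation and switching. It also plans the proportion dosed in accordance with the label, in the whole study population and in the renal subset.

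**The concern.** The objectives are defined by why the drug was prescribed, and the cohort by whether the patient has ever had an AF code. The two coincide only if every AF-coded patient who starts a DOAC in general practice starts it for AF.

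The plan itself treats the source cohorts as wider than NVAF, since NVAF patients have to be picked out of them. If an AF-coded patient receives a DOAC for venous thromboembolism or after joint replacement, the first such prescription becomes the index date. Its dose is then judged as NVAF dosing, and a planned short course counts as short duration or early discontinuation. Section 7 gives the study of compliance with labelling as a reason for monitoring use, so the accordance table is where this matters most.

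**Working it through.** **Is there an indication check anywhere?** I compared the definition with the other places where one could sit.

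- Entry and exclusion rules (section 9.1, Table S2): first prescription, prior use of the index drug, same-day entry to two cohorts, AF record, valve replacement or mitral stenosis. None concerns another indication.
- Variables (section 9.3): neither venous thromboembolism nor joint replacement is listed.
- Code lists (Annex 3): drugs, AF, mitral stenosis, valve replacement, dialysis, kidney transplant and CKD stages. DVT appears only among the abbreviations in section 2.
- Table 1 (section 9.7): the row for another indication refers to a reason for lowering the dose, not to another condition being treated.
- Limitations (section 9.9): misclassified indication is not mentioned. Hospital prescribing is stated not to be captured.
- AF codes (Table S3): these include resolved AF and a history of AF, with no time limit, so a remote AF code is enough.

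Nothing closes the gap.

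**Scale.** The plan gives no figure to reproduce, so this is an illustration. Let *s* be the share of the NVAF cohort whose index prescription was for another indication, *p* the true non-accordance among stroke-prevention users, and *a* the proportion of other-indication users classed as non-accordant. All three are assumptions.

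Reported non-accordance = (1 − s) × p + s × a

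| s | p = 10%, a = 50% | p = 10%, a = 100% | p = 20%, a = 50% | p = 20%, a = 100% |
|---|---|---|---|---|
| 1% | 10.4% | 10.9% | 20.3% | 20.8% |
| 5% | 12.0% | 14.5% | 21.5% | 24.0% |
| 10% | 14.0% | 19.0% | 23.0% | 28.0% |

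For example, with s = 5%, p = 10% and a = 100%: 0.95 × 10% + 0.05 × 100% = 14.5%. The bias is s × (a − p), so it is upward only if a exceeds p.

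**Against sampling error.** Section 9.5 cites an earlier CPRD study with 1589 naïve rivaroxaban users and 541 naïve apixaban users. The 95% half-width is 1.96 × √(p(1 − p)/n).

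- n = 1589: 1.5 points at p = 10%, 2.0 at p = 20%.
- n = 541: 2.5 points at p = 10%, 3.4 at p = 20%.

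At s = 1% the bias is 0.3 to 0.9 points, below these half-widths. At s = 5% it is 1.5 to 4.5 points and at s = 10% it is 3 to 9 points. A share of 5-10% can therefore equal or exceed sampling error.

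**Early discontinuation.** Let *d* be true early discontinuation. If every other-indication user stops early, the reported figure is (1 − s) × d + s. The overstatement is s × (1 − d), and this is the maximum. With an assumed d of 30% it is 0.7 points at s = 1%, 3.5 at s = 5% and 7 at s = 10%.

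**The case against.** The best reply is that the problem may be small. Section 9.9 says hospital prescriptions are not captured, so a course supplied wholly by a hospital, as some post-operative courses may be, cannot create an index date. The documents are as compatible with a 1% share as with 10%, and at 1% the effect is lost in sampling error. That stands. It limits the size but does not remove GP-issued courses.

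The reply also counts against several stronger readings that a reader might infer.

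- *That all other-indication use is non-accordant.* No label text is in the protocol, so a = 100% is an upper bound and 14.5% or 19% is a worst case.
- *That early discontinuation is inflated by the full share s.* This holds only if no true stroke-prevention user stops early. The bound is s × (1 − d).
- *That listing every strength in Table S1, such as "Rivaroxaban 10mg tablets", is itself a fault.* A study of label accordance must capture unusual strengths, or it would hide the dosing it sets out to describe.
- *That every objective is affected alike.* The third primary objective (renal impairment) and the secondary objective (time trends) refer to NVAF patients prescribed DOACs without naming stroke prevention, so for their wording the AF-based definition fits. A distorted trend would also need a changing mix of indications, on which the documents are silent.
- *That such patients should simply be excluded.* AF and venous thromboembolism can coexist, and a DOAC may then serve both. Exclusion as the main definition would remove some legitimate stroke-prevention users.

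**Conclusion.** The mismatch is real. Sections 8.1 (first two primary objectives) and 9.1.1 target use for stroke prevention, while section 9.1 and Table S2 identify AF-coded starters for any reason. The definition is fixed in the protocol and stated twice, so it is not detail left to an analysis plan.

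It bears on dose, label accordance, duration and discontinuation. Its size cannot be derived from the documents and may be modest. The figures above rest on assumed values of s, p, a and d and show only when the effect would matter: hardly at 1%, potentially as much as or more than sampling error at 5-10%. The conclusion also takes as given that some GP-issued DOAC courses are for venous thromboembolism or follow joint replacement. As written, the study could not tell a reader which case applies. The point concerns cohort classification only and implies nothing about which dose is right.

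**What to change.** 1. Add to Annex 3 a code list for DVT/PE and hip/knee replacement.
2. Flag, rather than exclude, NVAF patients with such a record in a fixed window around index. Three months before to 2 weeks after is one option, with the end matching the AF window. The length is a judgement and should be set before extraction.
3. Report the number flagged by drug and calendar year. This also shows whether the mix changed over the enrolment period.
4. Present the main dose, accordance and duration tables, including discontinuation, with and without flagged patients.
5. Add possible misclassification of indication to section 9.9, noting that indications outside the code list remain undetected and that hospital-issued courses are not seen.

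The cost is one more code list and a second set of the main tables, with no new data source. Some flagged patients will be true stroke-prevention users with a coincident event, which is why both versions are shown.
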